6.2. Exclusion criteria

1. Prior immune checkpoint therapy with an anti-PD-1, anti-PD-L1, anti-CD137, or anti-CTLA-4 antibody.
2. Known severe hypersensitivity [Grade ≥ 3 NCI CTCAE 5.0] to investigational product or any component in its formulations, any history of anaphylaxis, or recent, within 5 months, history of uncontrollable asthma.
3. Previous malignant disease (other than the target malignancy to be investigated in this study) within the last 3 years. Participants with a history of cervical carcinoma in situ, superficial or noninvasive bladder cancer, localized prostate cancer or basal cell or squamous cell carcinoma in situ previously

treated with curative intent and endoscopically resected GI cancers limited to the mucosal layer without recurrence in > 1 year are NOT excluded.

4. Active central nervous system (CNS) metastases and/or carcinomatous meningitis that require therapeutic intervention or are causing clinical symptoms. Patients with previously treated brain metastases may participate provided they are stable and are not using steroids for at least 7 days prior to randomization.
5. Prior major surgery within 4 weeks prior to the first dose of study intervention.
6. Unstable or unresolved surgical or chemotherapy-related toxicity that would compromise the patient's capacity to participate in the trial. Persisting Grade > 1 NCI CTCAE 5.0 toxicity (except alopecia and vitiligo) related to prior therapy; however, sensory neuropathy Grade \leq 2 is acceptable.
7. Prior organ transplantation including allogenic stem-cell transplantation, except transplants that do not require immunosuppression.
8. Live vaccines given 30 days prior to first dose of protocol treatment (M7824). Seasonal flu vaccines that do not contain a live virus are permitted. Also, COVID-19 vaccines approved by the authorities that do not contain live virus are permitted.
9. Drug-induced interstitial lung disease (ILD) or participant has had a history of drug-induced pneumonitis that has required oral or IV steroids, and/or other diseases, which in the opinion of the Investigator might impair the participant's tolerance for the study or ability to consistently participate in study procedures.
10. Active and serious autoimmune disease that might deteriorate upon treatment with immunotherapy. Patients with diabetes type I, vitiligo, psoriasis, or hypo- or hyperthyroid diseases not requiring immunosuppressive treatment are eligible. Replacement therapy (i.e. thyroxine, insulin, or physiologic corticosteroid replacement therapy for adrenal or pituitary insufficiency, etc.) or topical therapy (e.g., steroids) for psoriasis or eczema is not considered a form of systemic treatment.
11. Ongoing clinically serious infections requiring systemic antibiotic or antiviral, antimicrobial, or antifungal therapy.
12. Known history of active tuberculosis or any active infection requiring systemic therapy.
13. Patients with diagnosed immunodeficiency or receiving systemic steroid therapy or any other form of immunosuppressive therapy within 7 days prior to enrollment, EXCEPT for the following: a. intranasal, inhaled, topical steroids, or local steroid injection (e.g., intra-articular injection); b. Systemic corticosteroids at physiologic doses \leq 10 mg/day of prednisone or equivalent; c. Steroids as premedication for hypersensitivity reactions (e.g., CT scan premedication).
14. Clinically significant (i.e., active) cardiovascular disease: cerebral vascular accident/stroke (< 6 months prior to enrollment), myocardial infarction (< 6 months prior to enrollment), unstable angina, congestive heart failure (\geq New York Heart Association Classification Class II), or serious cardiac arrhythmia requiring medication.

15. History of bleeding diathesis or recent major bleeding events within 12 months prior to enrollment (i.e. Grade ≥ 2 bleeding events in the month prior treatment)
16. History of abdominal or tracheoesophageal fistula, active gastrointestinal ulcer or gastrointestinal perforation within 12 months prior to enrollment
17. Patients with any serious underlying medical condition that might impair patient's capacity to participate in the trial.
18. Substance or alcohol abuse, medical, psychological or social conditions that may interfere with the patient's participation in the trial or evaluation of the trial results.
19. Women who are pregnant or in the period of lactation.

7. Patient enrollment

The patients will be eligible for the study after reviewing by the site's staff all the inclusion and exclusion criterion. This trial will use a web-based enrollment system (eCRF-Electronic Case Report Form). Each participating centre will access the system directly to enroll the patients.

Patient eligibility needs to be checked before enrollment of the patient in the Fundación GECP web-based system (eCRF). The dates of the patient signature of the Informed Consent of the study and the specific informed consent to tumor tissue and blood samples are required to be filled in the eligibility checklist of the eCRF.

The treatment should start preferably the date of enrollment or within 1-5 days from the date of enrollment.

8. Trial procedures

8.1. Overview of treatment sequence

8.1.1. Baseline visit:

The following procedures must be performed 28 days before enrollment:

1. Sign the informed consent form
2. Demographic data including age and gender and medical relevant history, including comorbidities and allergies, surgeries, cancer history (including prior cancer therapies and procedures), reproductive status and smoking history.
3. To register whether patients experienced weight loss $\geq 5\%$ in the previous 3 months or since mesothelioma diagnosis.

4. Complete physical examination **including skin inspection** and collection of: Height, weight, ECOG performance status, Temperature and blood pressure and oxygen saturation.
5. Laboratory testing must be performed within 14 days before the enrollment and includes:
 - **Hematology and coagulation:** White blood cells (WBC) count, neutrophils, haemoglobin, platelet count, PT, INR and APTT.
 - **Biochemistry:** Ca, Mg, Na, K, Glucose, ALT, AST, LDH, total bilirubin, alkaline phosphatase, creatinine and clearance of creatinine calculated by Cockcroft-Gault formula, total protein, albumin, amylase, lipase.
 - **Thyroid function:** thyroid-stimulating hormone (TSH). Total or free T3 and total or free T4 must be analyzed if TSH result is out of ULN or LLN.
 - **HIV / Hepatitis B/C test:** The following local laboratory assessments should be done within 28 days prior to first dose: Hepatitis B and C testing (HBVsAg, HBV Ab and HCV Ab) and HIV test. In patients with positive hepatitis B/C results, HBV DNA/HCV RNA must be performed (Hepatitis B vaccinated patients are excluded).
 - **Pregnancy Tests:** A serum or urine pregnancy testing is required within 8 days prior to study enrollment.
 - **Urine test:** A urine testing (dipstick is allowed) is required within 3 days prior to study enrollment.
6. Electrocardiograms: A 12-lead ECG is required at screening and as clinically indicated. ECGs should be obtained on the same machine whenever possible. Lead placement should be as consistent as possible. ECG recordings should be performed after the patient has been resting in a supine position for at least 10 minutes. For safety monitoring purposes, the investigator must review, sign, and date all ECG tracings. Paper copies of ECG tracings will be kept as part of the patient's permanent study file at the site. Any morphologic waveform changes or other ECG abnormalities must be documented on the eCRF.
7. Baseline symptoms within the sign of study's Informed Consent will be recorded.
8. Medications (e.g. prescription drugs, over-the-counter drugs, vaccines, herbal or homeopathic remedies, nutritional supplements) from 7 days prior to initiation of study treatment (day 1 cycle 1) will be recorded.
9. Tumor assessment must be done within 28 days before enrollment (+ 10 days):

- **Chest and abdomen CT SCAN** with oral/IV contrast (unless contraindicated) to determine measurable disease according to modified RECIST v1.1.

10. Correlative studies (exploratory analysis):

- Blood samples will be drawn before day 1 of week 1 of treatment
- Pleural effusion liquid (when feasible) before day 1 of weeks 1 of treatment

8.1.2. Patient registration and enrolment

After baseline visit, the enrollment of the patient will be done in the Fundación GECP web-based system (eCRF). The dates of the patient signature of the Informed Consent of the study and the specific informed consent to tumor tissue and blood samples are required to be filled in the eligibility checklist of the eCRF.

8.1.3. Bintrafusp alfa (M7824) treatment

Day 1 of week 1 of treatment will start within 1-5 days from enrollment. Treatment will be administered every 2 weeks (± 3 days) until progression or other reason to discontinue. If a pseudoprogression is suspected patient is allowed to continue treatment until loss of clinical benefit as judged by principal investigator and after the permission from the trial chair is granted.

On Day 1 and Day 14 of each cycle (QW2), all eligible patients will receive:

Bintrafusp alfa (M7824): 1200mg, IV infusion over 60 minutes

Current experience revealed that IRRs to bintrafusp alfa occur seldomly and are generally mild to moderate in severity. Therefore, administration of a premedication is generally not required. If an Investigator deems necessary to administer a premedication to a particular participant, an antihistamine (e.g. 25 to 50 mg diphenhydramine) and paracetamol (acetaminophen, 500 to 650 mg intravenously or equivalent oral dose) is recommended. Premedication should be administered for subsequent bintrafusp alfa doses based upon clinical judgment and presence/severity of prior infusion reactions. This regimen may be modified based on local treatment standards and guidelines as appropriate provided it does not include systemic corticosteroids.

Management of symptoms should follow the guidelines shown in section 11.2.

The following procedures must be performed on day 1 of every 2/4 weeks (± 3 days):

1. Every 2 weeks: Physical examination, including skin inspection and collection of: weight, ECOG, Temperature, blood pressure and oxygen saturation.
2. Every 2 weeks: Blood pressure must be taken always before the drug administration. Blood pressure should be routinely measured before every infusion after a resting period of 10 min. If baseline record is performed more than 3 days before first study dose, they must be repeated on day 1 week 1.
3. Laboratory testing prior to each dose administration within 3 days prior to day 1 administration of each 4 weeks (note that for the first 3 months of treatment, haematology and biochemistry must be done every 2 weeks). If baseline testing is performed more than 3 days before first study dose, they must be repeated on day 1 week 1:
 - **Hematology and coagulation:** WBC count, neutrophils, haemoglobin, platelet count, PT, INR and APTT.
Note that coagulation must be done only if clinically indicated.
 - **Biochemistry:** Ca, Mg, Na, K, Glucose, ALT, AST, LDH, total bilirubin, alkaline phosphatase, creatinine and clearance of creatinine calculated by Cockcroft-Gault formula, total protein, albumin, amylase, lipase.
 - **Thyroid function:** thyroid-stimulating hormone (TSH). Total or free T3 and total or free T4 must be analyzed if TSH result is out of ULN or LLN.
 - **Pregnancy Tests:** A serum or urine pregnancy testing is required every 4 weeks during treatment.
 - **Urine test:** A urine testing (dipstick is allowed) must be done during treatment only if clinically indicated.
4. Adverse events: Changes from baseline symptoms (new or worsened clinically significant ones) should be recorded as adverse events on the Adverse Event form of the eCRF. For laboratory parameters, only grade 2 events will be reported as an AE. All the other events not related to laboratory values will be reported from grade 1.
5. Concomitant medications: Changes from baseline should be recorded on the eCRF.
6. Tumor assessment will be done every 8 weeks (\pm 7 days) from cycle 1 week 1. CT SCAN must be performed until progression disease or until last dose of bintrafusp alfa in case of continuing beyond pseudoprogression. The CT SCAN schedule will be maintained even if a delay in administration occurs.
 - **Chest and abdomen CT SCAN** with oral/IV contrast (unless contraindicated) to determine measurable disease according to mRECIST v1.1.

7. Correlative studies (exploratory analysis):

- Blood samples will be drawn at first tumor assessment

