- Keratoacanthoma
- Cutaneous squamous cell carcinoma (cSCC)
- Basal cell carcinoma
- Actinic keratosis

Management

- Baseline skin assessment with detailed medical history
- Discontinuation or termination not required in most cases. Continuation of treatment should be evaluated by the Investigator.
- Emollients may be used
- Develop diagnostic and treatment plan in collaboration with Investigator and dermatologist
- Treatment follow-up will depend on number and localization of lesions.
 - Single lesion: full excision may be recommended
 - Multiple lesion or location not suitable for full excision: Mohrs surgery, cryotherapy or other standard treatment options depending on pathology. Topical retinoids may be used after discussion with Investigator.
- Close clinical follow-up for re-evaluation, resolution and potential recurrence should be implemented
- In general, treatment of TGF- β mediated skin lesions should be based on local guidelines/standard of care.

Additional consideration: Keratoacanthoma lesions may resolve spontaneously without surgical intervention within weeks after discontinuing bintrafusp alfa.

Consult with Medical Monitor as needed for management of TGF- β mediated skin lesions.

Management of Anemia

- Anemia is considered an important identified risk for bintrafusp alfa.
- Hematology assessment must be performed at baseline, prior to each bintrafusp alfa dose, at the end of treatment visit and at 28 (± 5 days) days post-treatment safety follow-up.
- Participants must enter the study with Hgb values at least 9g/dl
- All relevant hematological testing for treatment-related anemias should be done prior to a blood transfusion, if clinically feasible

Basic Anemia Evaluation

- CBC with emphasis on red cell indices
- If indicated and at clinical discretion, the following should be considered:
 - Iron studies
 - Serum Folate and Vit B12 values
 - Coagulation factors
 - Fecal occult blood
 - Urinalysis
 - Hormone panel: TSH, Erythropoietin
 - Peripheral blood smear

Further Recommendation Based on Suspected Etiology (in Addition to Basic Anemia Testing)

- Suspected Hemolysis
 - bilirubin, LDH, Coombs test, haptoglobin
- Suspected bleeding:
 - Consider imaging/interventional radiology consultation as indicated
 - Consider imaging and/or endoscopy as clinically indicated
- Suspected aplastic anemia:
 - Hematology consultation
 - Consider bone marrow aspiration/morphologic evaluation

Additional consideration:

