| 
In case of rapid decrease of hemoglobin (Hgb), such as a decrease greater than 2.0 g/dL across a 2 weeks period, withhold the subsequent cycles of study intervention until Hgb is stabilized and do a thorough assessment of bleeding (for example, upper and lower GI endoscopy, enhancement CT etc.); if Grade 1 or greater bleeding is observed or suspected, withhold the bintrafusp alfa until the bleeding is resolved/controlled and resume the dose of bintrafusp alfa reduced by 50%. Once Hgb decrease is recovered to \leq Grade 1 or baseline and stably controlled, the Investigator is encouraged to communicate with Medical Monitor to re-escalate the dose. The dose of bintrafusp alfa may be re-escalated to full dose once Hgb is stabilized without further need for blood transfusion in the subsequent cycles. The timing of re escalation may need a case-by-case decision. See Section Table on Management of anemia | |
| Tumor Bleeding | |
| Grade \geq 2 | 
Study treatment must be held till the event recovers to Grade \leq 1Permanently discontinue treatment if the Investigator considers the participant to be at risk for additional severe bleeding. |
| Grade \geq 3 | 
If Grade \geq 3 bleeding event had been observed, regardless of causality with the study intervention, upon resumption of the study intervention bintrafusp alfa dose should be reduced by 50%. Once there is stable resolution and no recurrence of bleeding on reduced dose, Investigator is encouraged to communicate with the sponsor potential dose re-escalation after careful benefit-risk assessment. Treatment should be permanently discontinued if the Investigator considers the participant to be at risk for additional severe bleeding.In case of rapid decrease of hemoglobin (Hgb), see Section Mucosal/Non-Tumor bleeding. |

Impaired Wound Healing

- Impaired wound healing is considered important potential risk for bintrafusp alfa
- Management should be discussed with Medical Monitor for participants requiring surgery on study.
- It is recommended to hold study intervention for approximately 4 weeks post major surgery for observation.
- Post-operative wound healing should be closely monitored

12. Prohibited and permitted concomitant treatments

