13.1. Definition of an Adverse Event (AE) and AE's reporting

The main criterion for tolerability is the occurrence of toxicities and Adverse Events (AEs). [REDACTED]

[REDACTED]

[REDACTED]

[REDACTED]

[REDACTED]

[REDACTED]

An adverse event can therefore be any of the following:

Any unfavorable and unintended sign (including an abnormal laboratory finding) (see **NOTE 1** below), symptom, or disease temporally associated with the use of a medicinal product, whether or not considered related to the medicinal product.

Any new disease or exacerbation of an existing disease (a worsening in the character, frequency, or severity of a known condition), except events that are clearly consistent with the expected pattern of the disease progression. These data will be captured as efficacy assessment data only. If there is any uncertainty as to whether an event is due to disease progression, it should be reported as an adverse event.

Recurrence of an intermittent medical condition (e.g., headache) not present at baseline.

Any deterioration in a laboratory value or other clinical test (e.g., ECG, X-ray) that is associated with symptoms or leads to a change in study treatment or concomitant treatment or discontinuation from study drug.

Adverse events that are related to a protocol-mandated intervention, including those that occur prior to assignment of study treatment (e.g., screening invasive procedures such as biopsies).

Adverse events that occur during or within 24 hours after study drug administration and are judged to be related to study drug infusion should be captured as a diagnosis (e.g., "infusion-related reaction" or "anaphylactic reaction") on the Adverse Event eCRF. If a patient experiences both a local and systemic reaction to the same dose of study drug, each reaction should be recorded separately on the Adverse Event eCRF. Associated signs and symptoms should be recorded on the dedicated Infusion-Related Reaction eCRF.

A pre-existing medical condition should be recorded as an adverse event only if the frequency, severity, or character of the condition worsens during the study (e.g., "more frequent headaches").

NOTE 1: Abnormal laboratory and vital signs values:

A laboratory test result must be reported as an adverse event if it is a change from baseline and meets any of the following criteria:

Is accompanied by clinical symptoms,

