The AE severity grade provides a qualitative assessment of the extent or intensity of an AE, as determined by the investigator or as reported by the patients. The severity grade does not reflect the clinical seriousness of the event, only the degree or extent of the affliction or occurrence (e.g., severe nausea, mild seizure), and does not reflect the relationship to study drug.

Severity grade for other adverse events not covered in the toxicity grading scale:

| | |
|-------------|------------------|
| 1 = Grade 1 | Mild |
| 2 = Grade 2 | Moderate |
| 3 = Grade 3 | Severe |
| 4 = Grade 4 | Life-threatening |
| 5 = Grade 5 | Fatal |

However, depending on the SAE term used, there is some AE that do not have all the grades (e.g., the SAE term Alopecia only has the Grade 1 and 2).

The causal relationship to study drug is determined by the physician and should be used to assess all AE. The causal relationship can be one of the following:

Related: There is a reasonable causal relationship between study drug administration and the AE.

Not related: There is not a reasonable causal relationship between study drug administration and the AE.

The term "reasonable causal relationship" means there is evidence to suggest a causal relationship.

About the AEs that must be recorded in the eCRF note that:

- Baseline symptoms will be recorded on the eCRF and changes and updates in grade as well as resolution of an AE during treatment must be reported,
- An AE should be reported for each SAE notified,
- AEs should not be reported in a narrative description.

AEs can be spontaneously reported or elicited during open-ended questioning, examination, or evaluation of a subject (to prevent reporting bias, subjects should not be questioned regarding the specific occurrence of one or more AEs).

Any AE must be reported by an entry in the eCRF within 5 days of awareness, even if they do not meet the whole information. The diagnosis of the event should be recorded as AE term. If there is a secondary AE separated in time from the initiating event, it should be recorded as an independent event (e.g., if vomiting results in severe dehydration, both events should be reported separately).

13.2. Definition of Serious Adverse Event (SAE) and Suspected Unexpected Serious Adverse Reaction (SUSAR)

A Serious Adverse Event (SAE) is defined in general as any undesirable medical occurrence/adverse drug experience that occurs [REDACTED]

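### Section 8.1.3 contradicts itself and Section 11.2 on pre-dose haematology after month 3, and its laboratory adverse event rule (repeated in 8.1.5) conflicts with 13.1 NOTE 1

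*Combined protocol and SAP*

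**What the plan says.** **Haematology.** Section 8.1.3 gives bintrafusp alfa on days 1 and 14 of each 28-day cycle, so every 2 weeks for as long as treatment lasts. Its item on laboratory tests asks for "Laboratory testing prior to each dose administration within 3 days prior to day 1 administration of each 4 weeks" and adds in parentheses: "note that for the first 3 months of treatment, haematology and biochemistry must be done every 2 weeks".

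Section 11.2, under management of anaemia, says: "Hematology assessment must be performed at baseline, prior to each bintrafusp alfa dose, at the end of treatment visit". It sets no time limit. The bleeding guidance in the same section gives as its example of a rapid haemoglobin fall: "such as a decrease greater than 2.0 g/dL across a 2 weeks period, withhold the subsequent cycles of study intervention until Hgb is stabilized".

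**Laboratory adverse events.** Section 8.1.3 states: "For laboratory parameters, only grade 2 events will be reported as an AE". The next sentence reads: "All the other events not related to laboratory values will be reported from grade 1". Section 8.1.5 repeats the rule for the safety follow-up visit.

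Section 13.1 NOTE 1 says: "A laboratory test result must be reported as an adverse event if it is a change from baseline and meets any of the following criteria". The criteria are accompanying symptoms, a change in study treatment, a medical intervention or change in concomitant therapy, or clinical significance as judged by the investigator. No grade is mentioned.

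**The concern.** After month 3 the two halves of the 8.1.3 sentence describe different schedules: before each dose means 2-weekly, and day 1 of each 4 weeks means 4-weekly. The parenthesis has a purpose only if testing later becomes less frequent, so a coordinator could reasonably settle on 4-weekly counts. Section 11.2 does not allow that. Counts 4 weeks apart cannot show a fall over 2 weeks, and the mid-cycle dose would already have been given. Section 11.2 treats anaemia as an identified risk of the drug, and its response to a rapid fall is a hold, a bleeding work-up and, if bleeding is seen or suspected, resumption at half dose.

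The grade rule for laboratory events literally excludes grades 3 and 4. It is probably a slip for grade 2 and above, because the sentence after it sets a lower bound for all other events. As written, though, sites could record grade 2 only, grade 2 or higher, or any grade meeting NOTE 1. CTCAE-graded adverse events are a secondary endpoint, and laboratory counts collected under different rules do not pool cleanly.

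**Working it through.** The plan states no figure on this point, so there is none to reproduce. The check sets the rules side by side and then sizes the haematology gap.

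**Rules compared**

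| Topic | Visit instructions | Other rule | Compatible? |
|---|---|---|---|
| Haematology, first 3 months | 8.1.3: every 2 weeks | 11.2: before each dose | Yes |
| Haematology, after month 3 | 8.1.3: before each dose, and also day 1 of each 4 weeks | 11.2: before each dose | Not if 8.1.3 is read as 4-weekly |
| Laboratory AE, grade 1 meeting NOTE 1 | 8.1.3 and 8.1.5: not reported | 13.1 NOTE 1: must be reported | No |
| Laboratory AE, grade 3–4 meeting NOTE 1 | Literal wording: not reported | 13.1 NOTE 1: must be reported | No, unless grade 2 or higher was meant |
| Laboratory AE, grade 2 not meeting NOTE 1 | Reported | 13.1 NOTE 1: does not require it | Rules differ |

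**Dose count**

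- Dosing every 2 weeks for at most 2 years: weeks 0, 2, …, 102, which is 52 doses.
- Doses after month 3: 46 if 3 months is taken as 12 weeks, 45 if 13 weeks.
- Mid-cycle doses among them, with no required count under the 4-weekly reading: weeks 14, 18, …, 102. That is (102 − 14)/4 + 1 = 23 either way.

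**Average per patient**

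Inputs: median PFS of 3 months (null) and 4.5 months (alternative) and 47 patients, all from Section 16. Assumptions: exponential PFS, treatment until progression or 2 years, no treatment past suspected pseudoprogression, no skipped doses. One month is 365.25/12/7 = 4.348 weeks.

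S(t) = exp(−ln 2 × t / median). The expected number of uncovered doses is the sum of S over the 23 mid-cycle weeks, which equals S(week 14) × (1 − r²³)/(1 − r), where r is the survival factor over 4 weeks. Expected total doses are the sum of S over all 52 dosing weeks.

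| Quantity | Median 3 months | Median 4.5 months |
|---|---|---|
| r | 0.8085 | 0.8679 |
| S(week 14) | 0.475 | 0.609 |
| (1 − r²³)/(1 − r) = uncovered doses per patient reaching week 14 | 5.2 | 7.3 |
| Uncovered doses per patient, all patients | 2.46 | 4.43 |
| Expected total doses | 9.9 | 14.3 |
| Share of doses uncovered | 25% | 31% |
| Across 47 patients | 116 | 208 |
| S(24 months) | 0.4% | 2.5% |

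The maximum of 23 doses is therefore rare.

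**What still catches severe laboratory events**

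NOTE 1 requires a report for any change that alters treatment or needs intervention. Section 13.2 NOTE 3 makes a laboratory abnormality an SAE if, among other grounds, it interrupts or stops the drug or needs specific corrective therapy. Section 13.1 adds: "An AE should be reported for each SAE notified". Most grade 3–4 laboratory events would come in by one of these routes.

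**The case against.** **One practice satisfies every section.** A site that tests before each dose breaches nothing; a site that tests 4-weekly breaches 11.2. The stricter rule can be said to govern, which makes this an editorial ambiguity. The first part is true, but the site has to notice the stricter rule. Section 8.1.3 refers to 11.2 only for managing symptoms, not for test timing.

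**The 2-week fall is an example.** A large drop between 4-weekly counts could still be judged rapid, and examination, blood pressure and oxygen saturation are done every 2 weeks regardless. This stands as a limit: a fall could still be acted on, but later, and the plan's own example could not be assessed.

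**The risk label varies.** Section 3.3 lists anaemia as a potential risk, whereas 11.2 calls it identified. True, but either label supports the count that 11.2 requires.

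**The sizes are conditional and lean high.** They apply only where sites adopt the 4-weekly reading, and they ignore stops for toxicity or patient request and skipped doses. This stands. Adding the Section 16 dropout hazard of 0.04, assumed to be monthly and to end treatment, lowers the averages to about 1.9 and 3.2 doses. The lower bound is zero.

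**The AE rule is a slip with backstops.** Largely accepted. The conflict over grade 1 events that meet NOTE 1 remains after the slip is corrected.

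**Redaction.** The Section 2 schedule and the opening of 13.1 are largely blacked out and may contain a clear rule. That could guide sites, but it would not remove the contradictions in the visible text.

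**Conclusion.** Both points hold on the visible text. For haematology, the size lies between zero, if every site follows 11.2, and about 2.5 to 4.4 uncovered doses per patient on average if every site reads 8.1.3 as 4-weekly after month 3. Early stopping and skipped doses would lower the upper figures. The burden falls on the 47–61% of patients still on treatment at week 14, at about 5 to 7 doses each.

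For laboratory adverse events, the expected harm is inconsistent recording in the secondary safety endpoint, rather than wholesale loss of severe events.

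Neither point touches the primary PFS analysis, the sample size or the decision rule. The change should be made because a safety check for a recognised risk of the drug ought not to depend on which section a site reads. Confidence is medium, because the trial schedule could not be seen.

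**What to change.** 1. In 8.1.3, state that haematology is done before every bintrafusp alfa dose throughout treatment. Keep the 4-weekly timing for the other tests after month 3 if that is intended.
2. In 8.1.3 and 8.1.5, report as adverse events laboratory changes of grade 2 or higher, or of any grade meeting Section 13.1 NOTE 1. This keeps the plan's evident grade 2 threshold, so it retains some grade 2 values that NOTE 1 alone would not require.
3. Check that the Section 2 schedule and the eCRF completion guidance say the same.

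The cost is a wording clarification and eCRF guidance. Compared with 4-weekly testing, it adds one blood count per 4 weeks after month 3, at dosing visits patients already attend. Under the assumptions above that is about 116 to 208 counts across 47 patients, all of which 11.2 already requires.
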